#### Measures:

- Rates of completion of exercises (recorded by study trainer).
- Successful use of ActiGraph accelerometer.
- Patient rating of immediate outcomes on 10-point Likert scale: Ease of completion, overall utility, change in positive affect and optimism from pre- to post-exercise.

The intervention will be considered feasible if  $\geq 7$  of the 12 sessions are completed by a majority of patients. The objective assessment measures will be considered feasible if we obtain adequate physical activity data (at least 5 valid days of accelerometer wear time) in at least 80% of enrolled participants at one of the follow-up time points. The PP exercises will be considered to be acceptable if participants have mean scores of at least 6/10 on the ratings of ease of completion and subjective helpfulness across exercises. The PP exercises will be considered to have adequate impact if participants rate positive affect and optimism significantly higher post-exercise than pre-exercises across exercises (via mixed linear models).

**Aim #2** (*overall impact on psychological health*): To examine the intervention's impact on both positive (positive affect, optimism) and negative (depression, anxiety) psychological health, compared to TAU and a MI-based educational control condition.

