## **II. SPECIFIC AIMS**

**Specific Aim #1 (Feasibility [primary outcome], acceptability, immediate impact):** To assess the feasibility, acceptability, and immediate impact of the PP-based health behavior intervention

on optimism and happiness in a three-arm (N=75), randomized, controlled pilot trial.

*Hypothesis: The PP intervention will be feasible (the majority of participants will complete at least 7 of 12 sessions/exercises) and acceptable (mean score of at least 6 out of 10 on ratings of ease of completion and subjective helpfulness of the exercises) and will have adequate immediate impact on positive affect and optimism (post-exercise ratings of positive affect and optimism will be higher than pre-exercise ratings (measured by pre- and post- measurements on a Likert scale).*

**Specific Aim #2 (overall impact on psychological health):** to examine the intervention's overall impact on both positive (positive affect, optimism) and negative (depression, anxiety) psychological health, compared to TAU and an MI-based educational control condition.

*Hypothesis: The intervention will lead to significant pre-post increases in positive affect and optimism and significant reductions in depression and anxiety. Compared to the control conditions, the PP-based intervention will lead to greater numerical improvements in all psychological outcomes.*

**Specific Aim #3 (adherence and functional outcomes):** To examine the impact of the intervention on physical activity (steps, as measured by accelerometer; primary health behavior outcome), medication adherence, sodium intake, HF-related QoL, and generic HRQoL, compared to TAU and an MI-based educational control condition.

*Hypothesis: The intervention will lead to significant pre-post improvements in adherence and functional outcomes at follow-up and will lead to greater numerical improvements in these outcomes compared to the treatment as usual and the MI-based control condition.*

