### **C. Treatment assignment/randomization**

Participants will be randomized to receive one of three conditions: (1) the PP-based intervention, (2) an MI-based educational control condition, or (3) TAU. They will be randomized by a random-number generator and will be assigned a condition after Actigraph data is checked and has been found to be adequate at in-hospital Visit #2. The research assistant (RA)/blinded assessor who will conduct the follow-up assessments will be blind to the study condition. The interventionist and subjects will not be blind to the study condition.

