#### **Second Visit (Week 2; in person).**

At the second in person visit, which will take place one week after the initial visit, we will collect the Actigraph from participants, and check to ensure participants had at least 5 valid days of data. At this point, participants will be randomized to one of the three conditions noted above. Patients in the TAU group will receive no further intervention and will be scheduled for a follow-up appointment in 12 weeks. Participants in the PP and goal-setting or MI-only conditions will be provided with a manual corresponding to their treatment condition, as well as a copy of *Learning to Live with Heart Failure*, a practical guide which is provided by MGH to all HF patients admitted to a cardiology unit at MGH.

**PP and goal-setting intervention:** The trainer then will introduce the participant to the PP and goal-setting portions of the intervention. For the PP portion, participants will be assigned the first exercise (Gratitude for Positive Events) and will be instructed to perform the exercise within the next week. Prior to completing the exercise, participants will be asked to rate their current level of happiness and optimism, using a 10-point Likert scale. Immediately after completing the

exercise, participants will rate the ease of exercise completion, overall utility of the exercise, and their current levels of happiness and optimism, all using 10-point Likert scales. For the first goal-setting session, the trainer will discuss the importance of physical activity in HF. Participants will be given a pedometer, which participants will use to monitor the number of steps they take daily over the following week. The trainer will instruct them in its use and set a goal for monitoring their baseline physical activity over the next week. This pedometer will not be used as an outcome measure but simply will be a tool that participants can use to monitor their activity.

*MI-based educational intervention:* Participants in the MI-only control group will similarly have the rationale of the MI-based health behavior program explained to them, and will be assigned the first exercise. They also will be given a pedometer for their personal use. We estimate that this portion of the visit will take approximately 20 minutes.

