### Follow Ups:

**Follow-up phone calls (Week 12 and Week 24 [post randomization]).** At Weeks 12 and 24, a member of the study staff will call participants to repeat the self-report questionnaires that were administered at baseline. These questionnaires assess state optimism (State Optimism Measure; SOM), general optimism (LOT-R), positive affect (PANAS), overall health behavior adherence (MOS), anxiety/depression (HADS), HRQoL (SF-12), cardiac symptoms and HF-related QoL (KCCQ), medication adherence (SRMA), and sodium intake (SSQ). Participants will also be asked about cardiac-related hospital readmissions and cardiac rehabilitation, and to rate their overall satisfaction with the treatment they received for their cardiac condition over the course of the study on a scale of 0 (not at all satisfied) to 10 (completely satisfied). Finally, patients will be asked about their experience in the study, including any aspects of the intervention or study procedures that could be improved, during follow-up assessment. In sum, these scales should take approximately 30-40 minutes to complete. If participants would rather complete the follow-up questionnaires in written form rather than over the phone, we will send them a paper packet at the time of the follow-up.

**Training.** [name] (PI) has substantial experience in explaining and delivering PP exercises from their studies in cardiac and psychiatric patients. The PP exercises for this trial have been identified via published literature, or directly from researchers, and modified appropriately for this population. Additional text outlining the rationale and instructions for each exercise are located in the written packets for each exercise that are provided to participants. [name] will engage in several training exercises prior to study initiation. He will review the treatment manual and our team's prior training manuals related to these exercises. He will then complete all exercises to gain experience performing and reviewing each exercise.

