**(a) Physical activity (primary health behavior outcome measure).** We selected physical activity as our main health behavior outcome for several reasons. Physical activity is a key modifiable prognostic factor in HF patients and has been associated with improved exercise capacity, QoL, and survival in this population. Furthermore, there are established links between higher levels of positive emotions (particularly optimism) and increased physical activity, suggesting that a PP intervention could impact this behavior. Finally, increasing physical activity is likely to require a relatively broad approach, as compared to other behaviors, which may improve with simple interventions such as electronic reminders.

Physical activity will be measured using the ActiGraph GT3X+ three-axis accelerometer (ActiGraph, LLC, Pensacola, FL). Accelerometers are often considered to be the standard for measuring habitual physical activity. ActiGraph GT3X+ step counters are validated as measures of physical activity and have been used in numerous studies of physical activity in patients with medical illness. We chose to use ActiGraph GT3X+ accelerometers because they are the most widely used monitors for research purposes and adequately discriminate between different levels of activity. In this trial, participants will wear the accelerometer (for 1 week at baseline and 1 week at each follow-up time point) to assess the feasibility of doing so, ensure adequate capture of physical activity, and examine the impact of the intervention on this health behavior. We will measure the number of steps taken daily and the amount of time spent in moderate to vigorous physical activity (MVPA) to examine the impact of the intervention on these important outcomes. We will turn off all notifications on the device prior to the start of the study. We will require at least 480 minutes of wear time to be considered a valid day, and at least 5 valid days for a participant's data to be considered complete. If a participant does not provide at least this much data, we will ask the participant to re-wear the step counter until information from at least 5 valid days has been captured.

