**D. Power analysis**

We have performed power analyses assuming 20 participants in each group. To account for potential drop outs between enrollment and randomization, we will enroll 75 participants with a goal of randomizing 60. This pilot trial is not designed to detect significant between-group differences in 12- or 24-week health behavior outcomes, but is powered to meet our primary aims of feasibility and immediate impact. For feasibility, 75-80% of subjects have completed the majority of PP exercises in our prior work, and 90% completed the majority of PP exercises in our proof-of-concept trial in patients with HF. With 20 PP participants, we will have at least 80% power to detect a difference between our expected proportion of participants completing at least 5 out of 8 PP exercises (80%) and the null hypothesis (true proportion of 50% or less) at the

two sided 0.05 level using a binomial proportion test. In a prior study, we found that PP interventions led to a moderate ( $d=.52$ ) improvement in optimism immediately post-exercise. If we assume completion of ~140 exercises from 20 subjects and a within-person correlation of 0.5 for change in pre-/post- ratings across exercises, our proposed study is powered at over 80% to detect a similar effect size improvement of optimism immediately post-exercise at the two-sided 0.05 level.

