### **C. Outcomes Monitoring**

As noted above, this study is a pilot trial to determine if all aspects of the protocol are feasible, acceptable, and effective. After 12 participants have completed the trial, we will briefly review the study and our outcomes. If participants' acceptability scores in the PP group are low (or optimism scores decrease following the exercises), or we sense more generally that some participants have been dissatisfied with the program, we will likely alter the protocol to address these issues. Similarly, if our rates of session completion are far below expected rates, we will reassess our protocol and likely make substantial changes. We will then complete the more formal data analysis once 60 participants have completed the trial.

On a weekly basis, the research team will meet to review study progress. At that time, the principal investigator will review informed consent documents, study forms, and procedures completed that week, as well as all chart review forms performed that week for completeness and accuracy. The study team will also discuss any procedural difficulties, recruitment issues, and adverse events at this meeting (and before if needed). Investigators will also review consent documents and address acute issues in real time throughout the week. We will take several measures to ensure the integrity of data collection/entry/analysis and the fidelity of our intervention. [name] will periodically review the recordings of weekly phone calls to ensure their fidelity.

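### The accelerometer feasibility bar is a share of enrolled participants, so at the planned 75 enrolled and 60 randomized it is met only if all 60 randomized participants give adequate follow-up data

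*Combined protocol and SAP*

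**What the plan says.** Section VI.A and B (Aim #1, Measures) sets a criterion for the objective assessment measures, separate from the session-completion criterion. They are feasible if there are adequate physical activity data, defined as "at least 5 valid days of accelerometer wear time) in at least 80% of enrolled participants at one of the follow-up time points".

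Other sections fix who can contribute such data:

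- Section VI.D separates the two populations: "To account for potential drop outs between enrollment and randomization, we will enroll 75 participants with a goal of randomizing 60".
- Section IV.C places randomization after the baseline device check; a participant "will be assigned a condition after Actigraph data is checked and has been found to be adequate at in-hospital Visit #2". The Second Visit text in Section V.A agrees: staff "check to ensure participants had at least 5 valid days of data. At this point, participants will be randomized".
- The follow-up assessments are timed from randomization: "Follow-up phone calls (Week 12 and Week 24 [post randomization". Section V.A places follow-up accelerometer wear in the week after each of them.
- Section V.E provides for short wear: "we will ask the participant to re-wear the step counter until information from at least 5 valid days has been captured".
- Section VIII.C times the final analysis: "We will then complete the more formal data analysis once 60 participants have completed the trial".

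One place points the other way. Section II describes Aim 1 as carried out "in a three-arm (N=75), randomized, controlled pilot trial", which attaches 75 to the randomized trial. The project goals at the end of Section I do the same.

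**The concern.** The numerator can contain only randomized participants, because nobody else reaches Week 12 or Week 24. The denominator also contains people who left before randomization, and the plan expects 15 of them. Those 15 count as failures of follow-up wear although no follow-up wear was ever asked of them.

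The bar therefore mixes two quantities: loss before randomization, and success with the device at follow-up. At the planned numbers the first uses up the whole 20% allowance and leaves none for the second. The same follow-up performance could be labelled feasible or not feasible depending on how many people dropped out before Visit 2.

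At stake is the stated verdict on the device that supplies steps, the primary health behavior outcome. In a pilot meant to inform later trials, a wrong label on that measure could mislead.

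**Working it through.** **Inputs.** Threshold 80% of enrolled (VI.A and B). Planned enrolled 75, goal randomized 60, 20 per group (VI.D). Follow-up exists only after randomization (IV.C, V.A). The per-person probability *p* of giving adequate follow-up data is not in the documents and is varied below as an assumption.

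**The plan's own figures.** 3 groups × 20 = 60 randomized. The loss implied by 60/75 is 20%, and 60 / (1 − 0.20) = 75, so the enrollment figure reproduces. No stated number is miscalculated; the fault lies in applying the 80% to the enrolled count.

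**Count required.** 0.80 × 75 = 60. With 60 successes, 60/75 = 80.0%, which passes. With 59, 59/75 = 78.7%, which fails.

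**Rate required among the randomized**, 60/*n*, with 75 enrolled:

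| Randomized *n* | 60/*n* |
|---|---|
| 59 | 101.7% (impossible) |
| 60 | 100% |
| 65 | 92.3% |
| 70 | 85.7% |
| 75 | 80.0% |

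**Chance of meeting the bar as written**, P(X ≥ 60) with X binomial(*n*, *p*), participants independent, 75 enrolled:

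| *n* | *p* = 0.90 | *p* = 0.95 | *p* = 0.98 | *p* = 0.99 |
|---|---|---|---|---|
| 59 | 0% | 0% | 0% | 0% |
| 60 | 0.2% | 4.6% | 29.8% | 54.7% |
| 62 | 4.6% | 39.5% | 87.2% | 97.6% |
| 65 | 35.8% | 89.4% | 99.8% | >99.9% |
| 70 | 91.3% | 99.9% | >99.9% | >99.9% |
| 75 | 99.7% | >99.9% | >99.9% | >99.9% |

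At *n* = 60 the entry is simply *p* to the power 60; for example, 0.95^60 = 0.046.

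**Chance with randomized participants as the denominator**, at *p* = 0.90: 98.7% (48 of 59), 99.4% (48 of 60), 99.6% (52 of 65), 99.7% (56 of 70). The result hardly moves with the number randomized. The bar still discriminates: with 48 of 60 required, the chance of passing is 57.6% at *p* = 0.80 and 89.4% at *p* = 0.85.

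**Same data, opposite verdicts.** If 55 of 60 randomized participants give adequate data, that is 55/60 = 91.7% of the randomized (pass) but 55/75 = 73.3% of the enrolled (fail).

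**Sensitivity to enrollment.** If 60 were randomized from fewer enrolled, the bar would be 0.80 × 70 = 56 of 60 (93.3%) or 0.80 × 65 = 52 of 60 (86.7%). The plan states no rule that stops enrollment once 60 are randomized.

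**The case against.** **Little rests on this criterion.** It appears only in Section VI.A and B. It is not in the Aim 1 hypothesis, the feasibility definition in Section V.E, the statistical methods, the power analysis or the review triggers in Section VIII.C. The comparison of steps goes ahead whichever label results, and a reader can recompute the proportion from the counts. This stands, and it limits the weight of the point. It does not make the threshold correct.

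**Enrolled may have been meant as randomized.** Sections I and II do attach 75 to the randomized trial. But Section VI.D, in the same chapter as the criterion, separates the two terms explicitly. If randomized was meant, the word still has to change.

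**Counting the enrolled may be a deliberate, stricter choice.** Inadequate baseline wear bars randomization, so some of the loss before Visit 2 may itself be device failure. This is a fair point, and it means the verdict depends on follow-up wear as well as on early loss. But the plan gives no such rationale, and early drop-out for any other reason is counted in the same way.

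**Success may be very high.** Re-wear, payment tied to usable data and two follow-up time points may all raise *p*. They do not lower the required count of 60, and even at *p* = 0.99 the chance with 60 randomized is only 54.7%.

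**Exactly 60 randomized may be an edge case.** Waiting for 60 completers implies more than 60 randomized if anyone is lost afterwards. That would ease the bar, as the tables show. But if exactly 60 of 75 enrolled complete, all 60 must still have adequate data, unless a non-completer supplied Week 12 data.

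**Conclusion.** The concern holds. As written, the bar requires 60 successes from 75 enrolled, which is all 60 of the participants the plan aims to randomize. The counts follow from the plan's own figures; the probabilities rest on assumed, independent success rates. The 100% requirement applies at exactly 75 enrolled and 60 randomized. It eases if more are randomized or fewer enrolled, and becomes unreachable if 75 are enrolled and fewer than 60 randomized. It makes no difference whether the wording about one follow-up time point is read per person or for the whole cohort.

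This should be fixed, but its reach is limited: it affects a secondary Aim 1 label, not the primary session criterion, the sample size or the analysis of steps.

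**What to change.** In Section VI.A and B, make the denominator randomized participants: at least 80% of those randomized, which is 48 of 60 at the planned size, 52 of 65 or 56 of 70.

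Report the enrolled-to-randomized yield (planned 60/75) as a separate feasibility figure, with the number who failed the baseline wear requirement shown within it.

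The cost is one word and one reported figure. The drawback is that participants reach randomization only after adequate baseline wear, so the new denominator selects people who have already managed the device. The separate yield figure is needed to keep the baseline failures visible.

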#### Measures:

- Optimism: LOT-R; SOM
- Positive affect: PANAS (primary outcome measure for this aim)
- Anxiety/depression: HADS

We will examine between-group differences (PP-based condition vs. MI-informed educational control and PP-based condition vs. TAU) on changes in each of these psychological outcomes to assess the impact of the intervention compared to both an active control and TAU. The primary study endpoint will be 12 weeks, though we will secondarily assess the impact of the intervention on outcomes at 24 weeks as well.

**Aim #3 (Impact on functional outcomes and health behaviors):** To examine the impact of the intervention on physical activity (steps, as measured by accelerometer; primary health behavior outcome), medication adherence, sodium intake, HF-related QoL, and generic HRQoL, compared to treatment as usual and an MI-based health behavior education intervention.

**Measures:**

- HF-related QoL: KCCQ
- HF symptoms: KCCQ subscale
- Health related quality of life: SF-12
- Self-reported adherence: MOS
- Physical activity: ActiGraph accelerometer
- Medication adherence: SRMA
- Sodium intake: SSQ

We will examine between-group differences (PP-based condition vs. MI-informed educational control and PP-based condition vs. TAU) on changes in functional outcomes and health behaviors to assess the impact of the intervention compared to both an active control and TAU.

**C. Statistical methods**

Data will be downloaded from REDCap into the Stata statistical package. For Aim 1 (feasibility, acceptability), descriptive statistics will be used to report proportion of exercise completion and mean scores on exercise ratings of ease and utility. To examine the immediate impact of the intervention on positive affect and optimism, we will use linear mixed models (to account for within-person correlations) to examine the improvement in these scores from pre- to post-exercise.

For our secondary aims, we will initially compare physical activity (# of steps/day) at 12 and 24 weeks between groups using a Wilcoxon rank sum test, given that the distribution of the number of steps will likely be skewed. In addition, we will compare between-group differences in change over time in all self-report measures (including psychological, functional, and health behavior outcomes) at the 12 and 24-week time points using random effects regression models with a random intercept for each patient. All statistical tests will be two-tailed, with  $p < .05$  considered significant.

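### The immediate-impact mixed model rests on about 20 people, and the plan fixes neither small-sample inference nor the random effects; a normal-reference test would run at about 6.5–7.1% instead of 5% (minor)

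*Combined protocol and SAP*

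**What the plan says.** Section VI.A and B (Aim #1, Measures) counts the exercises as having adequate impact if "participants rate positive affect and optimism significantly higher post-exercise than pre-exercises across exercises (via mixed linear models"). Section VI.C gives the method: "we will use linear mixed models (to account for within-person correlations) to examine the improvement in these scores from pre- to post-exercise". On software it says "Data will be downloaded from REDCap into the Stata statistical package", and on testing "All statistical tests will be two-tailed", with p < .05 as the threshold.

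Section VI.D states "We have performed power analyses assuming 20 participants in each group". For immediate impact it assumes "completion of ~140 exercises from 20 subjects and a within-person correlation of 0.5" for the change in ratings. It claims more than 80% power at d = .52 for a "similar effect size improvement of optimism immediately post-exercise at the two-sided 0.05 level". The same section lists immediate impact with feasibility among the primary aims that the trial is powered to meet.

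Neither document section says whether this model is fitted by ML or REML, which reference distribution or degrees of freedom the test uses, or which random effects the model contains. A random intercept per patient is specified only for the between-group models of the secondary aims.

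**The concern.** Completion, accelerometer use and acceptability are judged against descriptive thresholds. Immediate impact is the one Aim 1 criterion decided by a p-value, so the calibration of that p-value matters.

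About 140 exercises come from about 20 people, and the plan itself assumes that changes within a person correlate at 0.5. The precision of the mean change is therefore governed by 20 person-level averages. A test that refers the estimate to a normal distribution treats the between-person variance as known. ML also understates that variance. Both errors make the p-value too small.

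The structure of the model raises a second issue. If it allows people to differ in their level but not in their change, the variation in change between people is largely left out of the standard error.

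**Working it through.** **Inputs.** From VI.D: n = 20 people, about 140 exercises (m = 140/20 = 7 each), correlation of change 0.5, d = 0.52, two-sided 0.05. Assumed, because the plan does not say: a normal-reference (z) test with either ML or REML.

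**1. The plan's power figure.** Design effect = 1 + (7 − 1) × 0.5 = 4. Effective n = 140/4 = 35. Noncentrality = 0.52 × √35 = 3.08.
- Normal reference: Φ(3.08 − 1.96) = 86.8%.
- Noncentral t, 19 df: 83.1%.

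Both exceed 80%, so the stated power reproduces.

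**2. Size of one two-sided test, with a person-level effect on change in the model.** With balanced data this is a one-sample problem on 20 person means.
- REML, z: 2 × P(t₁₉ > 1.960) = 6.5%.
- ML, z: the variance is too small by 19/20, so the size is 2 × P(t₁₉ > 1.960 × √(19/20)) = 2 × P(t₁₉ > 1.910) = 7.1%.
- If only 16 people contribute ratings: 6.9% (REML) and 7.7% (ML).

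Simulation of the balanced model (200,000 runs) with z tests gave 6.6% (REML) and 7.3% (ML) at correlation 0.5, and 6.2% and 6.8% at correlation 0.1. With t on 19 df, REML gave 4.7–5.1% over correlations 0.1–0.5. ML with t on 19 df still gave 5.6% at correlation 0.5, which is why REML is part of the fix. With unequal numbers of exercises (1–12 per person; 6,000 runs) the sizes were 7.2% (ML, z), 6.5% (REML, z) and 5.0% (REML, t).

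**3. Interval width at n = 20, relative to t₁₉ (critical value 2.093).**
- REML, z: 1.960/2.093 = 0.936, about 6% too narrow.
- ML, z: 1.910/2.093 = 0.913, about 9% too narrow.

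**4. What this means for the success rule.** Only an increase counts, so the relevant error per outcome is half the two-sided size: 7.1%/2 ≈ 3.6% under ML against a nominal 2.5%. If positive affect and optimism must both be significant, simulated joint false success under ML and z is 0.1%, 0.7% and 1.6% at between-outcome correlations of 0, 0.5 and 0.8.

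**5. Dependence on the random effects.** Take between-person and within-person variances of change of 1 each (correlation 0.5), and fit raw pre/post ratings with a person intercept only.
- True variance of the mean change: (1 + 1/7)/20 = 0.0571.
- Residual df: 280 ratings − 20 people − 1 = 259.
- Expected residual variance: each person's departure in change contributes ±½ of itself to 14 ratings, so (14 × ¼ × 19 + 0.5 × 259)/259 = 0.757.
- Variance the model reports: 2 × 0.757/140 = 0.0108.
- The standard error is too small by a factor √(0.0571/0.0108) ≈ 2.30, so the size is about 2 × P(Z > 1.96/2.30) ≈ 39%.

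A 300-run ML fit gave about 37% for intercept only and about 6% once a random slope for change was added. Other checks, which also had to assume the baseline spread, ranged over 33–48%. A t reference does not help, because with 259 df it is almost normal.

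**6. Aim 2–3 self-report models (60 people, 3 visits).** On the same assumption, 2 × P(t₁₁₄ > 1.960 × √(114/120)) ≈ 5.9%.

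**The case against.** The strongest reply is that silence on the estimator does not show that the wrong one will be used. The plan names a software package and no settings. ML with z tests is an assumption, and REML with t would give 5.0%. This stands, so the result is given as a range and the point is one of specification.

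A reader might infer that the adequate-impact rule itself exceeds its 5% error rate. The documents do not support that. The rule is directional and joins two outcomes with an and. Under the plain reading, false success is well below 5% even with ML and z. What remains wrong is each separate p-value.

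A reader might also infer that the inflation is the same however the random effects are written. It is not: the 6.5–7.1% holds only if change is allowed to vary between people.

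Two further limits stand. No confidence intervals are planned for this analysis, so the width figure concerns any that are later reported. No stated figure fails, since power stays above 80% on the t basis. Feasibility, the designated primary outcome, is reported descriptively and is unaffected.

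For Aims 2 and 3 the effect is too small to press. The between-group hypotheses there speak of numerical improvement, and VI.D says the pilot is not designed to detect between-group differences in health behavior outcomes.

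**Conclusion.** The omission is real and its effect on calibration is modest. If the test uses a normal reference and the model carries a person-level effect on change, each two-sided 5% test runs at about 6.5–7.1% with 20 people, or 6.9–7.7% with 16. Any 95% interval is about 6–9% too narrow at 20. In the success direction the ML figure is about 3.6% against 2.5% per outcome, and joint false success is below 2% for between-outcome correlations up to 0.8. The problem is miscalibrated p-values and intervals, not a rule whose overall error passes 5%.

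The larger exposure is the unstated random-effects structure, where an intercept-only fit to raw ratings would give roughly 33–48% false positives. The plan does not say that such a model will be used, but it does not exclude it. Severity: minor.

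**What to change.** In VI.C, state that the immediate-impact model is fitted by REML with a person-level random effect on the pre-post change (or, equivalently for this purpose, as a random-intercept model on change scores), with Kenward-Roger or Satterthwaite degrees of freedom, about 19 here, for tests and any intervals. Both parts are needed, because the degrees-of-freedom method alone does not repair an intercept-only model.

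In VI.D, quote power for optimism on the t basis: about 83% at d = .52.

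Using the same REML and degrees-of-freedom method for the Aim 2–3 self-report models is optional.

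The cost is one sentence and a model option. Sample size, data collection and conduct do not change. The only downside is a slightly less favourable power figure, 83% instead of 87%, which still meets the plan's claim.
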